The investigator will make an assessment of severity for each adverse event and serious adverse event reported during the study. The assessment of severity will be based on:

The **Common Terminology Criteria for Adverse Events**, version 4.03 which is available at the following location:
http://ctep.cancer.gov/protocolDevelopment/electronic_applications/ctc.htm.

Assessment of Causality

- The investigator is obligated to assess the relationship between investigational product and device and each occurrence of each adverse event/serious adverse event.
- Relatedness means that there are facts or reasons to support a relationship between investigational product and the event.
- The investigator will use clinical judgment to determine the relationship.
- Alternative causes, such as underlying disease(s), concomitant therapy, and other risk factors, as well as the temporal relationship of the event to study treatment administration will be considered and investigated.
- The investigator will also consult the Investigator's Brochure and/or Product Information, for marketed products, in his/her assessment.
- For each adverse event/serious adverse event, the investigator must document in the medical notes that he/she has reviewed the adverse event/serious adverse event and has provided an assessment of causality.
- There may be situations in which a serious adverse event has occurred and the investigator has minimal information to include in the initial report. However, it is very important that the investigator always make an assessment of causality for every event before the initial transmission of the serious adverse event data.
- The investigator may change his/her opinion of causality in light of follow-up information and send a serious adverse event follow-up report with the updated causality assessment.
- The causality assessment is 1 of the criteria used when determining regulatory reporting requirements.

Approved

Follow-up of Adverse Event and Serious Adverse Event

- The investigator is obligated to perform or arrange for the conduct of supplemental measurements and/or evaluations as medically indicated or as requested by Amgen to elucidate the nature and/or causality of the adverse event or serious adverse event as fully as possible. This may include additional laboratory tests or investigations, histopathological examinations, or consultation with other health care professionals.
- If a subject is permanently withdrawn from protocol-required therapies because of a serious adverse event, this information must be submitted to Amgen.
- If a subject dies during participation in the study or during a recognized follow-up period, the investigator will provide Amgen with a copy of any postmortem findings including histopathology.
- New or updated information will be recorded in the originally completed Event CRF.
- The investigator will submit any updated serious adverse event data to Amgen within 24 hours of receipt of the information.

Reporting of Serious Adverse Event

Serious Adverse Event Reporting via Electronic Data Collection Tool

- The primary mechanism for reporting serious adverse event will be the electronic data capture (EDC) system via the Safety Report Form.
- If the EDC system is unavailable for more than 24 hours, then the site will report the information to Amgen using an electronic Serious Adverse Contingency Report Form (see [Figure 12-1](#)) within 24 hours of the investigator's knowledge of the event.
- The site will enter the serious adverse event data into the electronic system as soon as it becomes available.
- After the study is completed at a given site, the EDC system will be taken off-line to prevent the entry of new data or changes to existing data.
- If a site receives a report of a new serious adverse event from a study subject or receives updated data on a previously reported serious adverse event after the EDC has been taken off-line, then the site can report this information on a paper Serious Adverse Event Report Form (see [Figure 12-1](#)).

Adverse Device Effects: Recording, Evaluating and Reporting

- Any adverse event resulting from an adverse device effect that occur during the study will be documented in the subject's medical records, in accordance with the investigator's normal clinical practice, and on the Event CRF page.
- It is very important that the investigator provides his/her assessment of causality (relationship to the medical device provided by Amgen) at the time of the initial report and describes any corrective or remedial actions taken to prevent recurrence of the incident.

Figure 12-1. Sample Electronic Serious Adverse Event Contingency Report Form

Completion Instructions - Electronic Adverse Event Contingency Report Form
(For use for clinical trial studies using Electronic Data Capture [EDC])

NOTE: This form is to be used under restricted conditions outlined on page 1 below. If you must fax an event report to Amgen, you must also enter that event into the EDC system (eg, Rave) when it becomes available.

General Instructions

The protocol will provide instruction on what types of events to report for the study. This form is to be used ONLY to report events that must be captured in the Amgen safety database. *Indicates a mandatory field.

Types of Events to be reported on this form

- Serious Adverse Events (regardless of causal relationship to IP)

1. Site Information

Site Number* – Enter your assigned site number for this study

Investigator*, Country*, Reporter*, Phone No., and Fax No. – Enter information requested

2. Subject Information

Subject ID Number* – Enter the entire number assigned to the subject

Age at event onset, Sex, and Race – Enter the subject's demographic information

End of Study date – If the subject has already completed the study or terminated the study early, enter the End of Study date

If you are submitting follow-up information to a previous report, provide the serious adverse event term for the previous report as well as the start date for the initial event.

3. Serious Adverse Event

Provide the date the Investigator became aware of this Information

Serious Adverse Event Diagnosis or Syndrome* –

- > If the diagnosis is known, it should be entered. Do not list all signs/symptoms if they are included in the diagnosis.
- > If a diagnosis is not known, the relevant signs/symptoms should be entered.
- > If the event is fatal, the cause of death should be entered and autopsy results should be submitted, when available.

Date Started* – Enter date the adverse event first started (not the date on which the event met serious criteria) rather than the date of diagnosis or hospitalization. This is a mandatory field.

Date Ended – Enter date the adverse event ended and not the date when the event no longer met serious criteria. If the event has not ended at the time of the initial report, a follow-up report should be completed when the end date is known. If the event is fatal, enter the date of death as the end date.

If event occurred before the first dose of Investigational Product (IP)/drug under study, add a check mark in the corresponding box.

Is event serious?* – Indicate Yes or No. This is a mandatory field.

Serious Criteria Code* – This is a mandatory field for serious events. Enter all reasons why the reported event has met serious criteria:

- > Immediately life-threatening – Use only if the subject was at immediate risk of death from the event as it occurred. Emergency treatment is often required to sustain life in this situation.
- > If the investigator decides an event should be reported in an expedited manner, but it does not meet other serious criteria, "Other Medically Important Serious Event" may be the appropriate serious criterion.

Relationship to IP – The Investigator must determine and enter the relationship of the event to the IP at the time the event is initially reported. This is a mandatory field.

Relationship to Amgen device* – The Investigator must determine and enter the relationship of the event to the Amgen device (e.g. prefilled syringe, auto-injector) at the time the event is initially reported. If the study involves an Amgen device, this is a mandatory field. This question does not apply to non-Amgen devices used in the study (e.g. heating pads, infusion pumps)

Outcome of Event* – Enter the code for the outcome of the event at the time the form is completed. This is a mandatory field.

- > Resolved – End date is known
- > Not resolved / Unknown – End date is unknown
- > Fatal – Event led to death

If event is related to a study procedure, such as a biopsy, radiotherapy or withdrawal of a current drug treatment during a wash-out period, add a check mark to the corresponding box. This does not include relationship to IP or concomitant medication – only diagnostic tests or activities mandated by the protocol.

4. Hospitalization

If the subject was hospitalized, enter admission and discharge dates. Hospitalization is any in-patient hospital admission for medical reasons, including an overnight stay in a healthcare facility, regardless of duration. A pre-existing condition that did

not worsen while on study which involved a hospitalization for an elective treatment, is not considered an adverse event. Protocol specified hospitalizations are exempt.

Approved

Completion Instructions - Electronic Adverse Event Contingency Report Form
(for use for Studies using Electronic Data Capture [EDC])

Note, this form is to be used under restricted conditions outlined on page 1 of the form. If you must fax an event report to Amgen, you must also enter that event into the EDC system (eg, Rave) when it becomes available.

At the top of Page 2, provide your Site Number and the Subject ID Number in the designated section.

5. **IP Administration including Lot # and Serial # when known / available.**
Blinded or open-label – If applicable, indicate whether the investigational product is blinded or open-label
Initial Start Date – Enter date the product was first administered, regardless of dose.
Date of Dose Prior to or at the time of the Event – Enter date the product was last administered prior to, or at the time of, the onset of the event.
Dose, Route, and Frequency at or prior to the event – Enter the appropriate information for the dose, route and frequency at, or prior to, the onset of the event.
Action Taken with Product – Enter the status of the product administration.
6. **Concomitant Medications**
Indicate if there are any medications.
Medication Name, Start Date, Stop Date, Dose, Route, and Frequency – Enter information for any other medications the subject is taking. Include any study drugs not included in section 5 (Product Administration) such as chemotherapy, which may be considered co-suspect.
Co-suspect – Indicate if the medication is co-suspect in the event
Continuing – Indicate if the subject is still taking the medication
Event Treatment – Indicate if the medication was used to treat the event
7. **Relevant Medical History**
Enter medical history that is relevant to the reported event, not the event description. This may include pre-existing conditions that contributed to the event allergies and any relevant prior therapy, such as radiation. Include dates if available.
8. **Relevant Laboratory Tests**
Indicate if there are any relevant laboratory values.
For each test type, enter the test name, units, date the test was run and the results.
9. **Other Relevant Tests**
Indicate if there are any tests, including any diagnostics or procedures.
For each test type, enter the date, name, results and units (if applicable).

At the top of Page 3, provide your Site Number and the Subject ID Number in the designated section.

10. **Case Description**
Describe Event – Enter summary of the event. Provide narrative details of the events listed in section 3. Include any therapy administered, such as radiotherapy; (excluding medications, which will be captured in section 6). If necessary, provide additional pages to Amgen.
Complete the signature section at the bottom of page 3 and fax the form to Amgen. If the reporter is not the investigator, designee must be identified on the Delegation of Authority form.

Approved

AMGEN Study # 20170703 AIMOVIQ (erenumab/AMG 334)	Electronic Serious Adverse Event Contingency Report Form For Restricted Use
---	--

Reason for reporting this event via fax

The Clinical Trial Database (eg. Rave):

- Is not available due to internet outage at my site
- Is not yet available for this study
- Has been closed for this study

<<For completion by COM prior to providing to sites: SELECT OR TYPE IN A FAX#>>

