The detection and documentation procedures for adverse device effects described in this protocol apply to all Amgen medical devices provided for use in the study (see [Section 7.1.3](#) for the list of Amgen medical devices).

Adverse Device Effect Definition

An adverse device effect is any adverse event related to the use of a combination product or medical device. Adverse device effects include adverse events resulting from insufficient or inadequate instructions for use, adverse events resulting from any malfunction of the device, or adverse events resulting from use error or from intentional misuse of the device.

Recording Adverse Events and Serious Adverse Events

Adverse Event and Serious Adverse Event Recording

- When an adverse event or serious adverse event occurs, it is the responsibility of the investigator to review all documentation (eg, hospital progress notes, laboratory, and diagnostics reports) related to the event.
- The investigator will then record all relevant adverse event/ serious adverse event information in the Event case report form (CRF).
- The investigator must assign the following adverse event attributes:
 - Adverse event diagnosis or syndrome(s), if known (if not known, signs or symptoms);
 - Dates of onset and resolution (if resolved);
 - Severity (or toxicity defined below);
 - Assessment of relatedness to investigational product (erenumab or placebo) or Amgen medical devices (prefilled syringes); and
 - Action taken.
- If the severity of an adverse event changes from the date of onset to the date of resolution, record as a single event with the worst severity on the Event CRF.
- It is not acceptable for the investigator to send photocopies of the subject's medical records to sponsor in lieu of completion of the Event CRF page.
- If specifically requested, the investigator may need to provide additional follow-up information, such as discharge summaries, medical records, or extracts from the medical records. In this case, all subject identifiers, with the exception of the subject number, will be blinded on the copies of the medical records before submission to Amgen.
- The investigator will attempt to establish a diagnosis of the event based on signs, symptoms, and/or other clinical information. In such cases, the diagnosis (not the individual signs/symptoms) will be documented as the adverse event/serious adverse event.

Approved

Evaluating Adverse Events and Serious Adverse Events

Assessment of Severity

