5.1.3 Safety Endpoints

Serious Adverse Event (SAE)

An event categorized as "Adverse Event" on the Events eCRF starting on or after signing of the informed consent and up to the End of Study date with the indicator flag "Serious" equal to "Yes".

Treatment-emergent Adverse Event

An event categorized as "Adverse Event" on the Events eCRF starting on or after first dose of investigational product, as determined by "Did event start before first dose of investigational product" equal to "No" or missing, and up to the End of Study date.

Serious Treatment-emergent Adverse Event

A treatment-emergent adverse event with the indicator flag "Serious" equal to "Yes" on the Events eCRF.

Treatment-emergent Adverse Device Effect

A treatment-emergent adverse event with the indicator flag “Is there a reasonable possibility that the event may have been caused by the investigational device” equal to “Yes” on the Events eCRF.

Treatment-related Treatment-emergent Adverse Event

A treatment-emergent adverse event with the indicator flag “Is there a reasonable possibility that the event may have been caused by Investigational Medicinal Product” equal to “Yes” on the Events eCRF.

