5.4 Study Time Intervals

5.4.1 Study Periods

The following data will be categorized into treatment periods. Any data occurred after EOS date will not be included in the analysis.

Efficacy Assessments at Scheduled Visits, Vitals

- DBTP: Study Day 1 to minimum (first OL dose date, EOS date)
- OLTP: (First OL dose date + 1) to EOS date

Adverse Events, Concomitant Medications

- DBTP: Study Day 1 to minimum (first OL dose date – 1, EOS date)
- OLTP: First OL dose date to EOS date

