8.3 Handling of Missing and Incomplete Data

Subjects may miss specific data points for a variety of reasons. In general, data could be missing due to a subject's early withdrawal from the study, a missed visit, or inability to evaluate an endpoint at a particular point in time. For this study, efficacy endpoints are clinical outcome assessments (COAs) collected via daily eDiary or monthly assessments at the office visits. Missing COAs with respect to quality-of-life questionnaires (MPFID, HIT-6, MFIQ, MIDAS, Sleep questionnaire, Allodynia symptom checklist, BDI-II, GAD-7 and PGIC) will not be imputed. **Missing items in each eCOA questionnaire will be handled based on the scoring algorithm for each COA.**

Subjects could miss entering several days of data in eDiary within each monthly interval. The calculation of monthly measurements about subjects' migraine and non-migraine headaches will be handled using the following method, also described in [Section 5.1.1](#).

- For each monthly interval with ≥ 14 days of eDiary use:

- Monthly frequency measurements will be prorated to 28-day equivalents. Prorated result does not need to be rounded.
- Monthly average scores will be calculated as the average of observed scores.
- For monthly intervals with < 14 days of eDiary use, all monthly measurements will be set as missing.

Missing safety endpoints will not be imputed **except for partial AE start dates**. Missing or incomplete dates will be listed as reported, except for incomplete start date of an AE or concomitant medication, which will be imputed as follows:

Missing	Imputation	Exception on adverse event start date
Day	01	Default to study day 1 if an adverse event started the same year and month as study day 1 and the flag indicates that the adverse event started on or after the first dose of investigational product on the Events eCRF
Day/Month	01 Jan	Default to study day 1 if an adverse event started the same year as study day 1 and the flag indicates that the adverse event started on or after the first dose of investigational product on the Events eCRF
Day/Month/Year	None	—

Similarly, incomplete dates of HRU will be imputed using the same imputation rule as above.

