9.6.2 Adverse Events

The Medical Dictionary for Regulatory Activities (MedDRA) version 25.1 or later will be used to code all events categorized as adverse events to a system organ class and a preferred term. All AEs will be graded using the Common Terminology Criteria for Adverse Events (CTCAE) Version 4.03. All AE summary tables described below will be summarized by treatment group using subject incidence for the DBTP and be repeated using exposure-adjusted subject incidence for **the DBTP and the OLTP**.

The subject incidence of AEs will be summarized by SOC in alphabetical order and PT in descending order of frequency for all treatment-emergent adverse events (TEAEs), serious AEs, **serious TEAE occurring on or after the COVID infection**, AEs leading to **discontinuation** of investigational product, fatal AEs, **device-related AEs**, and adverse events of interest (EOI) including

- Ischaemic Central Nervous System Vascular Conditions SMQ (Narrow)
- Ischaemic Heart Disease SMQ (Narrow and Broad)
- Peripheral Arterial Disease AMQ (Narrow)
- Hypertension SMQ (Narrow and Broad)
- Constipation AMQ (Narrow and Broad)
- Alopecias AMQ (Broad)
- **COVID-19 SMQ (Narrow)**

Subject incidence of EOI (standardized MedDRA queries [SMQ] and/or Amgen medical queries [AMQ]) will also be summarized according to their categories **by SOC in alphabetical order** and PT in descending order of frequency.

Subject incidence of all TEAEs, SAEs, AEs leading to withdrawal of investigational product, and fatal AEs will be tabulated by PT in descending order of frequency. In addition, summaries of all TEAEs occurring in at least 3% of the subjects by PT in any treatment arm will be provided **by PT** in descending order of frequency.

Summaries of all TEAEs and SAEs will be tabulated by SOC, PT, and grade.

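### Adverse events that start double-blind and worsen on open-label erenumab enter the double-blind tables at their open-label grade, because the SAP has no rule for events ongoing at the first open-label dose

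*Protocol*

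**What the plan says.** **Recording (Protocol Section 12.4, Appendix 4).**
- An event whose severity changes between onset and resolution is one entry: "record as a single event with the worst severity on the Event CRF". Action taken is listed as an attribute of the same entry.
- Follow-up goes to the same form: "New or updated information will be recorded in the originally completed Event CRF".
- The completion instructions for the contingency report form (Figure 12-1) keep the start date at first onset when an event later becomes serious: "Enter date the adverse event first started (not the date on which the event met serious criteria".

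**Counting (SAP).**
- Section 5.1.3 defines a treatment-emergent event as one "on the Events eCRF starting on or after first dose of investigational product". A serious treatment-emergent event is such an event with the serious flag set to yes.
- Section 5.4.1 gives the double-blind window for adverse events as "Study Day 1 to minimum (first OL dose date – 1, EOS date". The open-label window runs from the first open-label dose.
- Section 9.6.2 says: "Summaries of all TEAEs and SAEs will be tabulated by SOC, PT, and grade". It also tabulates events leading to discontinuation of investigational product.
- Section 9.6.1 analyses double-blind safety by randomized treatment.

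**Design (Protocol Section 5.1, SAP Section 3.1).** Double-blind completers may continue into the open-label period. Those from placebo then receive erenumab 70 mg or 140 mg; the others keep their dose.

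For vital signs in the open-label period the SAP sets a separate pre-open-label baseline (Sections 5.3 and 9.6.1). Adverse events have no counterpart.

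**The concern.** The recording rule fixes an event's date at its beginning and its grade at its worst point. The period split uses a single cut date. When the two points fall on opposite sides of the first open-label dose, the tables combine a double-blind date with an open-label outcome.

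In the erenumab arms that outcome at least arises on the same drug and dose. In the placebo arm it arises on a different treatment. The double-blind period is the trial's only placebo-controlled safety comparison, and it is read from raw counts because no safety testing is planned. A few misplaced grade 3 or serious events could therefore change how the tables read.

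**Working it through.** The documents give no figure on this point, so there is nothing to reproduce. The check is a trace through the rules, followed by simple proportions for scale.

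**Trace.** Take a placebo subject with a grade 1 event starting in week 22. After the switch to open-label erenumab it becomes grade 3 and serious in week 30.

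| Step | Rule | Result |
|---|---|---|
| Record | Protocol 12.4, single entry at worst severity | One record, grade 3 |
| Start date | Protocol 12.4, first onset | Week 22 |
| Seriousness | SAP 5.1.3, flag on the same record | Serious = yes |
| Period | SAP 5.4.1, split at first open-label dose | Double-blind |
| Column | SAP 9.6.1, randomized treatment | Placebo |

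The event enters the double-blind placebo tables as a grade 3 serious event.

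**Does this depend on how Section 5.4.1 is read?** That section gives date windows without saying that the date is the onset date. Allocation by onset is inferred from the definition in Section 5.1.3 and from the exposure-adjusted rate in Section 5.6, which stops the clock at onset of the first event.
- By onset: the event is in the double-blind tables and absent from the open-label tables.
- Counted in both periods while ongoing: the double-blind tables still carry the worst grade and the serious flag.

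The double-blind entry arises under either reading. Only the absence from the open-label tables depends on the first.

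**Scale of one event.** Inputs: 183 per arm in the nonopioid cohort and 46 in the opioid cohort (Protocol Section 10.1).
- Nonopioid cohort: 1/183 = 0.55 percentage points.
- Both cohorts: 1/(183 + 46) = 1/229 = 0.44 percentage points.

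**Who is exposed.** The sample size section assumes 20% dropout. That leaves 0.8 × 183 = 146.4 nonopioid subjects per arm, or 0.8 × 229 = 183.2 over both cohorts, before anyone declines the open-label period. Of these, only subjects with an event unresolved at the first open-label dose matter. The documents do not allow that number to be estimated.

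**Direction.** For illustration, assume the earlier chronic migraine study's serious-event rates (Protocol Section 3.1) of 1.8% on placebo and 1.3% on 140 mg, unscaled for the longer period here. With 183 per arm, expected counts are 183 × 0.018 = 3.3 and 183 × 0.013 = 2.4.

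| Events carried back | Placebo | 140 mg | 140 mg minus placebo |
|---|---|---|---|
| None | 1.80% | 1.30% | −0.50 |
| One, placebo only | 2.35% | 1.30% | −1.05 |
| One, 140 mg only | 1.80% | 1.85% | +0.05 |
| One in each arm | 2.35% | 1.85% | −0.50 |

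The sign of the distortion depends on which arm has more such events. Any-event incidence in the earlier study was 46.2% (70 mg), 48.7% (140 mg) and 34.2% (placebo). If unresolved events scaled with incidence, the erenumab arms would have 46.2/34.2 = 1.35 and 48.7/34.2 = 1.42 times as many candidates as placebo. Against that, only placebo subjects are newly exposed to the drug. The documents do not say which effect is larger.

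**The case against.** The strongest reply is that the rule treats all three arms alike. Everyone who enters the open-label period takes erenumab, so late worsening is carried back into the 70 mg and 140 mg columns too. This stands. A reader might infer that the rule hides harm by loading the placebo column; the documents do not support that, because the net direction is open.

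Other replies, and what remains of each:
- **Exposure is limited.** A reader might take all 229 placebo subjects as at risk. The open-label period is optional and restricted to double-blind completers, and an event that resolves and recurs falls outside the single-entry rule. Both limits stand.
- **Relative size.** It is tempting to express one event as a share of the expected placebo serious events. That divides an assumed event by a rate from a study reported at week 12, so it measures nothing in this trial.
- **Discontinuations are visible elsewhere.** The SAP has separate end-of-product pages for each period (Section 5.5) and reports reasons by period in disposition (Section 9.2). This is correct and makes discontinuation the weakest part of the point. The adverse event tables are still not tied to those pages.
- **The start-date instruction is for a fallback form.** It is, and that form also collects admission dates. The SAP's serious flag nevertheless sits on the same event record, without a date for seriousness.
- **The eCRF may hold grade-change dates.** Its completion instructions are not among the documents, so this is possible. The SAP does not use such dates.
- **The primary analysis is locked first.** Worsening after its data cutoff cannot enter those tables. Earlier worsening can, because early enrollees are already on open-label drug when the last nonopioid subject reaches week 24.

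Partial onset dates are a separate, minor matter. A missing day becomes the first of the month, with an exception only at study day 1 ("Default to study day 1 if an adverse event started the same year and month as study day 1"). A reader might want to impute to the first open-label dose instead; that would push true double-blind events out of the randomized comparison and replace one directional error with its opposite.

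**Conclusion.** The gap is real on the face of the text. For grade it follows directly from Protocol Section 12.4. For seriousness it follows from the single record together with the SAP's flag. For discontinuation it is an inference from the SAP's silence on which period's product is meant.

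Followed as written, the plan can place an erenumab-period outcome in the double-blind placebo column. Whether the same event also drops out of the open-label tables rests on reading Section 5.4.1 as allocation by onset date.

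Each such event is worth 0.55 percentage points of a 183-subject arm. How many there will be, and which way they tilt the comparison, cannot be determined from the documents. The effect is confined to descriptive tables. This is a worthwhile, inexpensive improvement, not evidence of a biased safety comparison.

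**What to change.** 1. **SAP Sections 5.1.3 and 5.4.1.** State that adverse events are allocated by onset date, that double-blind grade and seriousness are those reached before the first open-label dose, and that a double-blind-onset event that worsens or becomes serious on or after that dose counts as an open-label treatment-emergent event.
2. **Data to support it.** Add an exception to the single-entry instruction in Protocol Section 12.4 and the eCRF guidance, so that worsening on or after the first open-label dose is entered as a new record with its own date. Where grade-change dates were not captured, add a sensitivity table that leaves out of the double-blind tables the grade and serious flag of events ongoing at that dose. The as-written table can only overstate what was reached double-blind and the sensitivity table can only understate it, so together they bracket each arm's count.
3. **Discontinuations.** Assign an event leading to discontinuation to the period whose product was stopped, using the End of IP DBTP and End of IP OLTP pages.

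The cost is one eCRF instruction, a few SAP sentences and a small number of extra records. One episode may then appear once in each period, so a footnote should say that counts are not to be summed across periods. Item 3 uses data already collected.
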